6.1 Safety Population

The safety population is defined as all subjects who received study medication.

6.2 Pharmacokinetic Population

The PK population will include all subjects completing the study and for whom the PK profile can be adequately characterized.

Any subject with ELX-02 pre-dose concentration prior to ELX-02 administration on Day 1 will be presented in the listings of concentrations and pharmacokinetic data but excluded from the descriptive statistics and analysis of variance (ANOVA) tables if the pre-dose concentration is greater than 5% of the C_{max} value measured on Day 1 for that subject. Subjects withdrawn due to AEs or PK reasons will be analyzed and reported but excluded from the statistical analysis. However, the concentrations for these subjects will be included in the descriptive statistics.

Here are some aspects to be considered (but not to be limited to) when determining data availability for the PK population: inclusion and exclusion criteria, acceptable times for visit dates and measurements, compliance with treatment, the nature and quality of the data, withdrawal, and any protocol deviation. The final responsibility of deciding which subjects are to be included or excluded lies with the principal investigator and/or the Sponsor.

Following to the end of the clinical portion of the study, prior to the start of the analysis of the samples, subjects analysed for PK population will be established by the inVentiv Health project team and finalized after Sponsor's review, according to the SOP ANI 3550_4 (Use of the Confinement Report and Subjects To Be Analyzed Form). All information including: subject withdrawals, adverse events that could affect characterization of the PK profile, concomitant medications taken, deviations to dosing procedures, deviations to study restrictions and sample particularities/missing blood draw will be detailed in the Confinement Report and Subjects To Be Analyzed Form (CR/STBA form).

Eloxx Pharmaceuticals

7. Interim Analyses

No formal interim analysis was planned in the protocol. However, interim PK analyses will be conducted after completion of dosing of the mild (Group 1) and moderate (Group 2) RI patients in order to assess plasma and urine ELX-02 exposure prior to proceeding with administration to severe (Group 3) RI patients. In interim analyses, PK parameters will be calculated using scheduled sampling times as actual sampling times will not be available.

Mean ± SD plasma ELX-02 concentration versus time curves will be presented using linear and semi-log scales. Descriptive statistics for all PK ELX-02 primary and secondary parameters sorted by renal function group will be provided. Additional plots and/or analyses may be performed at the discretion of the kineticist.

8. Study Population and Exposure

Descriptive statistics will be used to present and summarize study population and exposure data.

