### 9.3 In-Patient Stay and Visit

Subjects will remain as in-patients from the morning of Day -1 until after the 72-hour post-dose blood draw. Subjects will come back for a follow-up visit on Day 8 (±1 day).

Participation of each subject in this study should last approximately 1 week (approximately 5 weeks including the screening visit).

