### **9.13 Subject Withdrawal and Replacement**

Subjects will be advised that they are free to withdraw from the study at any time. Over the course of the study, the Sponsor and the PI or a delegate may withdraw any subject from the study for one of the reasons described below; subject withdrawal will be done in accordance with the clinical site SOP:

- safety reason;
- non-compliance with protocol requirements;
- significant protocol deviation;
- positive alcohol test, cotinine test (Group 4 only), drug screen, or pregnancy test.

For RI subjects (Groups 1 to 3) taking medications allowed by the PI, a positive result to opiate/benzodiazepine/THC screen (drug screen) may derive from the use of the concomitant medications. The subjects will not be automatically withdrawn from the study but will be evaluated on a case-by-case basis by the PI.

Hematology, biochemistry, urinalysis, and coagulation results will be reviewed by the PI or a Sub-Investigator prior to dosing; subjects will be withdrawn from the study if it is deemed that the subject's safety may be at risk on the basis of these test results.

Subjects who withdraw or are withdrawn from the study after dosing, for reasons other than safety and tolerability, may be replaced in order to ensure a minimum of 6 completed subjects per group. The total number of subjects dosed (including potential replacement subjects) will remain within a maximum of 8 subjects per group and within a maximum of 32 subjects for the whole study. Additional replacement resulting in dosing more subjects than planned in this protocol would be documented in a protocol amendment.

Subjects who withdraw or are withdrawn will be asked to remain at the clinic until the PI or a delegate agrees that the subject is fine and can be discharged. As soon as subject withdrawal is confirmed, blood sampling will be stopped. A PK blood draw may be collected at the time of withdrawal if deemed required by the PI. Study exit procedures will be performed at the time of withdrawal from the study or as soon as possible thereafter.

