### **12.2.2 Pharmacokinetic Population**

The pharmacokinetic population will include all subjects completing the study and for whom the PK profile can be adequately characterized.

Data (concentrations and PK parameters) from subjects withdrawn due to AEs will be presented but excluded from descriptive statistics.

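### The PK population rule drops complete AUC0-24, Cmax, Tmax and Rmax values when a subject withdraws after 24 h; the effect is conditional and modest, and inclusion by parameter would remove it

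*SAP*

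**What the plan says.** Two rules decide who enters the PK comparison.

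- **Completion.** SAP 6.2: "The PK population will include all subjects completing the study and for whom the PK profile can be adequately characterized". Protocol 12.2.2 sets the same condition: "The pharmacokinetic population will include all subjects completing the study and for whom the PK profile can be adequately characterized". Neither document defines completion. The last scheduled contact is the Day 8 visit (protocol 9.3). SAP section 6 bases the PK analysis on this population.
- **Reason for withdrawal.** SAP 6.2 adds: "Subjects withdrawn due to AEs or PK reasons will be analyzed and reported but excluded from the statistical analysis". PK reasons are not defined and there is no qualifier for time. The SAP then keeps these subjects' concentrations in the descriptive statistics, so the exclusion must refer to the ANOVA and the Hodges-Lehmann comparison.

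SAP 6.2 also lists withdrawal among the aspects to weigh and adds: "The final responsibility of deciding which subjects are to be included or excluded lies with the principal investigator and/or the Sponsor". It gives no criterion.

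Three other provisions bear on this. SAP 10.3.1 bars AUC0-24 only if the 24 h concentration is missing, and AUC0-72 only if the 72 h concentration is missing. SAP section 4 moved the primary partial AUC from 0-72 h to 0-24 h. On replacement, protocol 9.13 says that subjects who withdraw after dosing "for reasons other than safety and tolerability, may be replaced in order to ensure a minimum of 6 completed subjects per group". SAP 3.4 makes no replacement the default and leaves exceptions to the Sponsor.

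**The concern.** The SAP judges the partial AUCs by parameter in section 10.3.1 but discards data by subject in section 6.2. In a single-dose study, what happens after a parameter has been fully observed cannot make that value invalid. A subject who leaves between 24 h and Day 8 still has a usable AUC0-24 and normally Cmax, Tmax and Rmax, all primary endpoints in SAP section 5.

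The losses that replacement does not routinely repair are those for safety and tolerability. If such withdrawals were linked to high exposure, dropping them would pull the ratio to control and its upper limit down, and so understate the effect of renal impairment. SAP 10.4 intends the results to inform dosing recommendations where clinically relevant.

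**Working it through.** **The plan's own figure.** Protocol 8.1 targets 6 completers in each of three impaired groups and 6 to 8 controls: 3 × 6 + 6 = 24 and 3 × 6 + 8 = 26. This reproduces the stated total of 24 to 26. There is no power or precision calculation to reproduce.

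**What is in hand when a subject leaves** (sampling times from protocol 9.9.1 and 9.9.2)

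| Time of leaving | Plasma samples | Post-dose urine intervals |
|---|---|---|
| just after 24 h | 9 of 13 | 6 of 9 |
| just after 72 h | 12 of 13 | 9 of 9 |

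Protocol 9.3 says: "Subjects will remain as in-patients from the morning of Day -1 until after the 72-hour post-dose blood draw". A subject who leaves the clinic on schedule and misses only Day 8 therefore lacks one plasma sample and no urine interval.

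**Is the peak captured by 24 h?** Protocol 5.2.2.2 gives, for healthy subjects at this dose, a median Tmax of 1.0 h and a half-life of 2.14 h. In a one-compartment first-order model (assumption), ke = ln 2 / 2.14 = 0.324 per h, and Tmax = ln(ka/ke)/(ka − ke) = 1.0 h gives ka = 2.27 per h. If elimination slows to 10% of normal, Tmax = ln(2.27/0.0324)/(2.27 − 0.0324) ≈ 1.9 h. Cmax and Tmax are thus normally observed well before 24 h. For Rmax, more than 78% of an SC dose was excreted within 12 h in healthy subjects (protocol 5.1.2), so the peak rate is normally early too.

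**Precision: one unreplaced loss.** The log-scale half-width is t(0.95, n + m − 2) × s × √(1/n + 1/m), with s = √ln(1 + CV²).

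- 6 controls: 1.8125 × √(1/6 + 1/6) = 1.046 with n = 6; 1.8331 × √(1/5 + 1/6) = 1.110 with n = 5. Ratio 1.061.
- 8 controls: 0.963 with n = 6 and 1.024 with n = 5. Ratio 1.064.

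Protocol 5.1.2 gives an AUC CV of 7.64% to 18.2% in healthy subjects, so s = 0.0763 to 0.1805. With 6 controls the upper-limit multiplier goes from 1.083 to 1.088 at the low CV and from 1.208 to 1.222 at the high CV.

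**Bias: the highest of 6 is lost (worst case, assumed).** The expected maximum of 6 standard normal values is 1.2672. Dropping it shifts the log mean of the other 5 by −(1.2672/5) × s = −0.2534 × s.

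| CV | s | Mean fall in geometric mean |
|---|---|---|
| 7.64% (documented, healthy) | 0.0763 | 1.9% |
| 18.2% (documented, healthy) | 0.1805 | 4.5% |
| 30% (assumed) | 0.2936 | 7.2% |
| 50% (assumed) | 0.4724 | 11.3% |

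A correlation of 0.5 between withdrawal and log exposure halves the log shift: 1.0% to 2.3% at the documented CVs. With no correlation the shift is zero. In 400,000 simulated trials with the highest of 6 always dropped, the 90% upper limit lay below the true ratio in 11.7% of trials, against about 5% with all 6 kept.

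**The case against.** The case for leaving the rule alone is fair in several respects.

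- **The event may be rare.** There is one dose, so no adverse event can stop treatment, and subjects are in-patients to 72 h. Adverse events are followed up under protocol 9.14.1 without requiring withdrawal. No rate is given. This stands.
- **The effect is small.** A loss unrelated to exposure only widens the interval slightly, and neither document states a boundary that a shift of this size could cross. This stands.
- **Safeguards exist.** The population is to be fixed before sample analysis, and excluded subjects are still reported. That limits data-driven choice but does not stop valid values being dropped. For Groups 1 and 2 the protection is less clear, because the interim PK analysis needs their assays before the clinical part ends.
- **Discretion could cover it.** It leaves some room for withdrawals for other reasons, but it gives no criterion and states no exception to the exclusion of AE withdrawals. SAP 10.4 permits additional analyses without committing to any.
- **Some parameters really are damaged.** Protocol 9.13 says: "As soon as subject withdrawal is confirmed, blood sampling will be stopped". After an early exit AUC0-t and Ae0-t can be truncated and AUC0-inf can rest heavily on extrapolation. This stands, and is why inclusion should be by parameter.

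A reader might go further and infer that the rule removes highly exposed subjects and so hides the effect of renal impairment. The documents do not support that. They show no link between withdrawal and exposure, and the auditory findings in protocol 5.1.2 do not rise with dose: one at 0.3 mg/kg IV judged unrelated, one at 5 mg/kg, none at 7.5 mg/kg.

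**Conclusion.** The point holds as a minor one. As written, the rule discards fully observed primary-endpoint values from a group of 6 for events after those values were obtained. For a withdrawal just after 24 h, four of the seven primary endpoints are normally affected without need: AUC0-24, Cmax, Tmax and Rmax.

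The size depends on such a withdrawal occurring and not being replaced. It is then about 6% in log-scale interval width, plus an average fall of 1.9% to 4.5% in the group geometric mean only if the lost subject is the highest of 6. The CVs come from healthy subjects; those in renal impairment may be larger. The 11.7% figure is conditional on the worst case and must not be read as the error rate of the plan. Day 8 as the end of the study is inferred from the schedule, since completion is undefined.

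**What to change.** In SAP 6.2, and in protocol 12.2.2 at its next amendment, replace the completion requirement and the exclusion for AEs or PK reasons with inclusion by parameter for every dosed subject:

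- AUC0-24: the 24 h sample is present. AUC0-72: the 72 h sample is present.
- Cmax and Tmax: sampled through the peak.
- Rmax: urine collected through the interval of peak excretion and at least one later interval.
- Ae0-t: planned urine collection complete.
- AUC0-t: sampling not cut short while concentrations were still quantifiable.
- AUC0-inf: Kel estimable and residual area within a limit stated in advance.

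Keep the exclusions for a pre-dose concentration above 5% of Cmax, for dosing deviations, and for "adverse events that could affect characterization of the PK profile", provided these events are documented before assay. Assay samples from all dosed subjects: protocol 11 now covers only the PK population and AE withdrawals, so another subject who leaves after 24 h might never be assayed. Report the present completers-only rule as a sensitivity analysis.

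The residual-area limit matters. With half-life = 2.14/(1 − Fe × (1 − g)), Fe = 0.811 to 0.992 from protocol 5.1.2 and GFR at g = 0.2 to 0.1 of normal (assumed), the half-life is 6.1 to 20.0 h. The extrapolated share after 24 h, 2^(−24/half-life), is then 6.5% to 43%.

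Costs: n will differ by parameter, there are a few extra assays and one more table, and the protocol wording change needs ethics committee approval unless it counts as administrative (protocol 14.1). AUC0-t would still lose subjects with slow elimination who leave early; AUC0-24 would not.

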## 7. Study Design

The study is a two-center, Phase 1, open-label, single-dose, one-period, four-parallel-group, PK study in subjects with various severities of renal dysfunction and healthy volunteers.

The subjects enrolled in the study will be categorized in 4 groups according to their renal function (eGFR value calculated using the MDRD4 equation – refer to section [9.2](#)):

- Group 1: subjects with mild renal impairment
- Group 2: subjects with moderate renal impairment
- Group 3: subjects with severe renal impairment
- Group 4 (control group): subjects with normal renal function

The mild (Group 1) and moderate (Group 2) patients with renal disease will be dosed first, in a parallel fashion. At this point, interim PK analyses will be performed and a safety committee composed of Sponsor and CRO members will jointly review the PK data. [REDACTED]

[REDACTED]  
[REDACTED]  
The safety committee will then authorize dosing in patients with severe renal disease (Group 3). Control subjects (Group 4) will be recruited after the recruitment of Groups 1 to 3 to facilitate subjects' matching between the healthy subjects in the control group with the RI subjects.

Each subject will receive a single SC dose of ELX-02 1 mg/kg on Day 1. They will remain as in-patients at the clinical site under close surveillance by the site staff for 72 hours post-dose and they will come back for a follow-up visit on Day 8 ( $\pm 1$  day).

Serial blood and urine samples will be collected to quantify ELX-02, in order to evaluate the effect of the various severities of renal impairment (i.e., mild, moderate, and severe renal impairment, as compared to a control group with normal renal function) on the PK of study drug. The study will also evaluate the safety and tolerability of ELX-02 in subjects with normal renal function and in RI subjects, by evaluating AEs, local reactions at the injection site, physical examination, vital signs, ECG, early markers of renal injury, and clinical laboratory parameters.

This study is intended for filing under FDA regulations.

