## 11. Analytical Methodology

Samples will be transported to the bioanalytical facility in at least two separate shipments, with each set of aliquots in separate shipments. Once the bioanalytical laboratory confirms receipt of the first shipment, the second set of aliquots may be sent. The samples should be packed on sufficient dry ice to keep them frozen for at least 72 hours.

All shipments will be accompanied by an inventory list and delivered to the following address:

Attn: Sample Coordination  
[REDACTED]  
[REDACTED]  
[REDACTED]  
[REDACTED]

Clinic personnel will notify the analytical laboratory prior to shipment by phone, fax or e-mail.

[REDACTED] will analyze ELX-02 in plasma and urine samples using validated methods.

The bioanalytical work in support to the study will be conducted in compliance with the GCP using the SOPs in place in the bioanalytical laboratory and as per applicable regulations.

Samples from subjects included in the PK population (see section 12.2.2) and from subjects who were withdrawn from the study due to AEs will be analyzed.

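### SAP 6.2 sets the PK population before sample analysis starts, but the interim requires Group 1 and 2 samples to be assayed while the study is still running

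*SAP*

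**What the plan says.** **Timing.** SAP 6.2 places the decision at one point for the whole trial: "Following to the end of the clinical portion of the study, prior to the start of the analysis of the samples".

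**Who decides.** In the same section, "subjects analysed for PK population will be established by the inVentiv Health project team and finalized after Sponsor's review". It also states: "The final responsibility of deciding which subjects are to be included or excluded lies with the principal investigator and/or the Sponsor".

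**On what basis.** The list of considerations is open. It begins "Here are some aspects to be considered (but not to be limited to) when determining data availability for the PK population" and takes in the nature and quality of the data and any protocol deviation. The information is recorded on the Confinement Report and Subjects To Be Analyzed (CR/STBA) form under a named SOP.

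**The interim.** SAP 7 says "interim PK analyses will be conducted after completion of dosing of the mild (Group 1) and moderate (Group 2) RI patients", and gives the purpose as "in order to assess plasma and urine ELX-02 exposure prior to proceeding with administration to severe (Group 3) RI patients". Its output is descriptive statistics by group for all primary and secondary PK parameters. Protocol 7 says "interim PK analyses will be performed and a safety committee composed of Sponsor and CRO members will jointly review the PK data", after which the committee authorises dosing of Group 3. Controls (Group 4) are recruited after Groups 1 to 3. Protocol 12 repeats the interim.

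**Which samples are assayed.** Protocol 11 limits assay to "Samples from subjects included in the PK population (see section 12.2.2) and from subjects who were withdrawn from the study due to AEs".

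**The concern.** Fixing the analysis population before concentrations exist keeps inclusion decisions independent of the results. Here that order is available for only part of the trial. By the time the form is due, the Group 1 and 2 results have been reported by group and reviewed by Sponsor and CRO members. The same two organisations establish and review the PK population, under criteria that leave room for judgement.

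At stake are the Mild/Control and Moderate/Control ratios, two of the three comparisons in SAP 10.4. In each, the impaired arm can be settled after its results are known and the control arm before assay. No rule ties the population used at the interim to the one used in the final analysis. SAP 4, which lists the changes from the protocol, does not address the point. SAP 10.4 says the study results may be used for dosing recommendations, so the selection should be seen to be independent of the data.

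**Working it through.** **1. The plan's own count.** Protocol 8.1 targets 6 completers in each of Groups 1 to 3 and 6 to 8 in Group 4: 3 × 6 + 6 = 24 and 3 × 6 + 8 = 26. This reproduces the stated 24 to 26.

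**2. The order of events.**

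- Groups 1 and 2 are dosed (Protocol 7).
- Their plasma and urine are assayed, and PK parameters are calculated and summarised (SAP 7).
- Sponsor and CRO members review the PK data, and Group 3 is then authorised (Protocol 7).
- Group 3 is dosed. Group 4 is recruited after recruitment of Groups 1 to 3.
- The clinical portion of the study ends.
- The PK population is set, before sample analysis starts (SAP 6.2).

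The second step comes before the fifth. For Groups 1 and 2 the population cannot be set both after the end of the clinical portion and before their samples are analysed. For Groups 3 and 4 it still can.

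**3. Share of subjects affected.**

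- As planned: 12/26 = 46% to 12/24 = 50%.
- With every group at the cap of 8: 16/32 = 50%.
- Extremes under the replacement caps: 12/(12 + 8 + 8) = 43% and 16/(16 + 6 + 6) = 57%.
- Within Mild/Control or Moderate/Control: the whole impaired arm, 6/(6 + 8) = 43% to 6/(6 + 6) = 50% of the subjects compared.
- Within Severe/Control: none, so far as the interim is concerned.

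**4. What one exclusion can do.** This is an illustration, not a forecast. Assume log-normal data, with log-scale SD σ = √ln(1 + CV²). The expected maximum of six standard normal values is 1.267. Removing it shifts the mean of the other five by −1.267/5 = −0.253 SD, so the ratio is multiplied by exp(−0.253σ).

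- CV 6.54% (lowest in Protocol 5.1.2, healthy subjects): σ = 0.065, ratio down 1.6%.
- CV 18.6% (highest there): σ = 0.184, ratio down 4.6%.
- CV 20% (assumed for impaired subjects): σ = 0.198, ratio down 4.9%.
- CV 30% (assumed): σ = 0.294, ratio down 7.2%.

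**5. Set against precision.** The standard error of the log difference is σ√(1/6 + 1/6) = 0.577σ with 6 controls and σ√(1/6 + 1/8) = 0.540σ with 8. The shift is 0.253/0.577 = 0.44 to 0.253/0.540 = 0.47 of a standard error. With 6 against 6 (10 degrees of freedom, t = 1.812), the 90% interval spans about 81% to 123% of the ratio at CV 20% and 74% to 136% at CV 30%. Because SAP 10.4 fits each comparison on its two groups alone, removing an extreme value would also tend to shrink that comparison's residual variance.

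**The case against.** A reader might infer that half the subjects will be selected with results known, and that the primary comparison is therefore biased. The documents do not support that. Several points count against it.

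- **Permission is not practice.** The plan allows results-aware decisions but does not require them. The form mainly records withdrawals, adverse events, concomitant medication, deviations and missing draws. These facts exist before assay and do not change when concentrations arrive. No rule permits exclusion for being extreme.
- **The contrast with Groups 3 and 4 is one of degree.** In every group some exclusions need assay data: a pre-dose concentration above 5% of Cmax, a profile that cannot be adequately characterised, or withdrawal for PK reasons. The first is a fixed numeric rule, and the blood schedule lists no pre-dose draw, so it may rarely apply.
- **The interim offers limited scope for steering.** It is descriptive and uses scheduled times. No control data need exist then, so no ratio to control need be visible. The documents do not say that the same individuals sit on the committee and complete the form.
- **The purpose of the timing rule is inferred.** It may be operational, deciding which samples to assay. Protocol 11 points to Protocol 12.2.2, which sets no end-of-study timing, so it adds only modest support.
- **The size is small** beside the confidence intervals, and SAP 10.4 calls the p-values exploratory.

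These points limit the consequence and leave the conflict in place. The SOP is not available and cannot be assumed to provide a staged form. Reading the timing group by group would remove the conflict, but SAP 6.2 refers to the clinical portion of the study as a whole.

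**Conclusion.** The timing rule in SAP 6.2 cannot be followed for Groups 1 and 2, 12 of 24 to 26 planned subjects. Discretionary decisions about them can be made with their PK results known, while those for Groups 3 and 4 can still precede assay. That is a gap in the safeguard for two of the three comparisons. It is not evidence of bias, since nothing shows that an exclusion would be driven by results.

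One exclusion of the highest value would lower the ratio by about 1.6% to 4.6% at the documented healthy-subject CVs. The figure of about 5% to 7% rests on an assumed CV of 20% to 30% in impaired subjects, which the documents do not give. Both take six subjects per impaired group and log-normal data. The conflict itself depends on none of these assumptions. It is worth correcting because the stated rule is unworkable and the remedy is cheap.

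**What to change.** Amend SAP 6.2 so that the CR/STBA form is finalised in two steps:

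1. For Groups 1 and 2, after their last visit and before their samples are released for interim assay.
2. For Groups 3 and 4, after their clinical portion and before their assay.

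Lock the decisions that rest on clinical and sample-handling facts at each step. Allow later exclusions only under the assay-dependent rules already in SAP 6.2 (pre-dose concentration above 5% of Cmax, profile not adequately characterised, PK reasons), applied in the same way to all four groups. List any change after a lock with its reason, and show the affected ratios with and without that subject. Refer to the first step in SAP 7, so that the interim and final populations are tied together.

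The cost is SAP wording, one extra use of an existing form, and less freedom to revise Group 1 and 2 inclusion later. Group structure, dosing and sample size are unchanged.
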